5.3.5.2 Gallbladder Ultrasound

Gallbladder data at each visit will be summarized and listed by treatment group. Shifts from baseline to last on-treatment (post-baseline) value will be presented for each evaluation.

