Furthermore, results from the thorough QT/QTc (TQT) study [CSOM230B2113] provided data on the QT/QTc intervals of a supra-therapeutic dose of pasireotide in healthy volunteers. The study was divided in two parts. In part 1, a maximum tolerated dose (MTD) of 1950 µg b.i.d. was identified. In part 2, the effects of pasireotide at MTD on the cardiac intervals were investigated. Pasireotide showed a peak effect on QTcF at 2 hours post-dose. There was a +10.0ms increase from baseline that correlates to a 17.5 msec difference versus placebo, while placebo had a -7.4 msec decrease from the baseline 2 hour post-dose. A similar effect was demonstrated on QTcI, but not observed on QTcB interval. Pasireotide subjects also showed a reduction of the heart rate at 0 to 4 hours post-dose with the maximum change versus baseline of 10.7 bpm.

A second thorough QT study [CSOM230B2125] is ongoing to further investigate the effect of pasireotide on QT/QTc intervals.

Study [CSOM230B2305] has shown that the safety profile of pasireotide is similar to other somatostatin analogues with the exception of hyperglycemia. As expected with effective treatment for Cushing's disease, some patients [13/162 (8%) randomized patients] experienced symptoms of hypocortisolism. No deaths were observed during pasireotide treatment, and the most frequently reported AEs included gastrointestinal AEs similar to approved somatostatin analogues: diarrhea (54.9 %), nausea (46.9%), cholelithiasis (29.6%), abdominal pain (20.4%). 70% of patients had at least one hyperglycemia-related AE.

2 Rationale

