8.2.2 Reporting

To ensure patient safety, every SAE, **regardless of suspected causality**, occurring after the patient has provided informed consent and until 28 days after the patient has stopped study treatment must be reported to Novartis within 24 hours of learning of its occurrence. Any SAEs experienced after this 28 days period should only be reported to Novartis if the investigator suspects a causal relationship to the study treatment. Recurrent episodes, complications, or progression of the initial SAE must be reported as follow-up to the original episode within 24 hours of the investigator receiving the follow-up information. An SAE occurring at a different time interval or otherwise considered completely unrelated to a previously reported one should be reported separately as a new event.

Information about all SAEs is collected and recorded on the Serious Adverse Event Report Form. The investigator must assess and record the relationship of each SAE to each specific study treatment (if there is more than one study treatment), complete the SAE Report Form in English, and send the completed, signed form by fax within 24 hours to the oncology Novartis Drug Safety and Epidemiology (DS&E) department.

[REDACTED]

The telephone and telefax number of the contact persons in the local department of Drug Safety and Epidemiology (DS&E), specific to the site, are listed in the investigator folder provided to each site. The original copy of the SAE Report Form and the fax confirmation sheet must be kept with the case report form documentation at the study site.

Follow-up information is sent to the same contact(s) to whom the original SAE Report Form was sent, using a new SAE Report Form stating that this is a follow-up to the previously reported SAE and giving the date of the original report. Each re-occurrence, complication, or progression of the original event should be reported as a follow-up to that event regardless of when it occurs. The follow-up information should describe whether the event has resolved or continues, if and how it was treated, and whether the patient continued or withdrew from study participation.

In addition, for Pasireotide s.c the following events are of special interest for targeted follow-up and should be notified to Novartis DS&E in the same manner as a SAE.

- Arrhythmogenic
- Bradycardia
- Coagulation
- Constipation
- Convulsions
- Diabetes insipidus
- Diarrhoea
- Gallbladder and biliary related AEs
- GI bleeding

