5.3.3 Laboratory abnormalities

The summaries will include all laboratory assessments collected no later than 28 days after study treatment discontinuation. All laboratory data will be listed and those collected later than 28 days after study treatment discontinuation will be flagged in the listings.

For laboratory tests covered by the Common Terminology Criteria for Adverse Events (CTCAE) version 3.0, the study's biostatistics and reporting team will grade laboratory data accordingly. For laboratory tests covered by CTCAE, a Grade 0 will be assigned for all non-missing values not graded as 1 or higher. Grade 5 will not be used. In the unlikely case when a local laboratory normal range overlaps into the higher (i.e. non-zero) CTC grade, the laboratory value will still be taken as within normal limits and assigned a CTC grade of zero.

For laboratory tests where grades are not defined by CTCAE, results will be graded by the low/normal/high classifications based on laboratory normal ranges.

Concentrations below the limit of quantification will not be presented in summary statistics.

The following summaries will be produced for the laboratory data (by laboratory parameter)

- Shift tables using CTCAE grades to compare baseline to the worst on-treatment value,
- For laboratory tests where CTCAE grades are not defined, shift tables using the low/normal/high classification to compare baseline to the worst on-treatment value,
- Shift tables of fasting glucose and related biochemical parameters using the [ADA \(2010\)](#) or similar low/normal/high classifications to compare baseline to the worst and last on-treatment value.

The following listings will be produced for the laboratory data:

- Listing of patients with laboratory values outside the laboratory reference ranges with values flagged to show the corresponding CTC grades and the classifications relative to the laboratory reference ranges,
- Listing of all laboratory data with values flagged to show the corresponding CTCAE grades and the classifications relative to the laboratory normal ranges.

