5.3.4 Vital signs

The parameters collected are: height (cm), weight (kg), body temperature (°C), pulse (beats per minute, bpm), systolic and diastolic blood pressure (mmHg).

The criteria for clinically notable abnormalities are defined as follows:

Clinically notable elevated values

- Systolic BP: ≥ 180 mmHg and an increase ≥ 20 mmHg from baseline
- Diastolic BP: ≥ 105 mmHg and an increase ≥ 15 mmHg from baseline
- Body temperature: $\geq 39.1^{\circ}\text{C}$
- Weight: Increase from baseline of $\geq 10\%$

- Pulse: ≥ 120 bpm with increase from baseline of ≥ 15 bpm

Clinically notable below normal values

- Systolic BP: ≤ 90 mmHg and a decrease ≥ 20 mmHg from baseline
- Diastolic BP: ≤ 50 mmHg and a decrease ≥ 15 mmHg from baseline
- Body temperature: $\leq 35^{\circ}\text{C}$
- Weight: decrease from baseline of $\geq 10\%$
- Pulse: ≤ 50 bpm with decrease from baseline of ≥ 15 bpm

The following summaries will be produced for each vital sign parameter:

- Summary statistic for change from baseline to the worst post-baseline value (in both directions, i.e. from baseline to highest post baseline and from baseline to lowest post-baseline value),
- Number and percentage of patients with at least one post-baseline vital sign abnormality (in both directions, i.e. both elevated and below normal values).

All vital sign assessments will be listed by vital sign parameter. Clinically notable values will be flagged on listings.

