5.3.5 Other safety data

5.3.5.1 ECG

The following analyses will be performed for HR, PR, QT intervals and QRS duration, ventricular rate, QTcB (Bazett's formula) and QTcF (Fridericia's formula):

- Summary statistics at baseline and all scheduled post-baseline time points,
- Summary statistics of changes from baseline at each scheduled post-baseline time point,
- Listing of ECG data (scheduled and unscheduled visits).

Number (%) of patients with a notable QT interval, based on both QTcB and QTcF, and newly occurring qualitative ECG abnormalities will be summarized at all scheduled post-baseline time points. A newly occurring ECG abnormality is defined as an abnormal post-baseline finding that was not present at baseline.

Notable criteria for QTcB/QTcF include:

- > 450 ms at any post-baseline scheduled time point and ≤ 450 ms at baseline,
- > 480 ms at any post-baseline scheduled time point and ≤ 480 ms at baseline,
- > 500 ms at any post-baseline scheduled time point and ≤ 500 ms at baseline,
- An increase from baseline > 30 ms at any post-baseline scheduled time point,
- An increase from baseline > 60 ms at any post-baseline scheduled time point.

A patient with multiple occurrences of a notable QT interval or a newly occurring ECG abnormality is counted only once in that category.

Patients with notable QT interval values and newly occurring qualitative ECG abnormalities will be flagged in the listings.

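### The gallbladder ultrasound shift table uses only the last on-treatment scan, so no planned table counts patients with any new ultrasound finding

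*SAP*

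**What the plan says.** SAP 5.3.5.2 (Gallbladder Ultrasound) has two sentences. The first plans a description over time: "Gallbladder data at each visit will be summarized and listed by treatment group". The second plans the comparison with baseline: "Shifts from baseline to last on-treatment (post-baseline) value will be presented for each evaluation". I take "each evaluation" in that sentence to mean each ultrasound item.

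The neighbouring safety sections use other conventions:

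- Laboratory data (SAP 5.3.3): "Shift tables using CTCAE grades to compare baseline to the worst on-treatment value". Fasting glucose and related parameters use ADA "or similar low/normal/high classifications to compare baseline to the worst and last on-treatment value".
- Vital signs (SAP 5.3.4): "Summary statistic for change from baseline to the worst post-baseline value", in both directions, plus the number of patients with at least one post-baseline abnormality.
- ECG (SAP 5.3.5.1): "A newly occurring ECG abnormality is defined as an abnormal post-baseline finding that was not present at baseline". A patient with several occurrences counts once per category.

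The protocol puts "Gallbladder and biliary related AEs" on its list of events of special interest (8.2.2). It has the ultrasound results recorded in the CRF (7.2.2.6). Its section on other safety data (10.5.2.4) sets no ultrasound analysis.

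**The concern.** Ultrasound is repeated through a long treatment period. The footnote to Protocol Table 7-1 continues it every 24 weeks after visit 13, and the SAP's visit windows run to week 156. A stone, sludge or duct change can appear at one scan and be gone at a later one. If only the last scan is set against baseline, that patient shows no new abnormality in the shift table.

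The question for a safety reader is how many patients developed a gallbladder abnormality on treatment. The shift table answers a different one: how many had an abnormality at the end. For an organ that the protocol singles out for targeted follow-up, both answers are wanted. The SAP gives no reason for treating ultrasound differently from its other repeated safety measures.

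**Working it through.** No figure in the plan depends on this choice, so there is none to reproduce. The check compares the planned displays and then asks which way the error can run.

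**1. Which display would count a new but transient finding?**

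| Display | Compares each patient with baseline? | Counts a finding absent at the last scan? |
|---|---|---|
| Ultrasound shift table (SAP 5.3.5.2) | Yes | No |
| Ultrasound by-visit summary (SAP 5.3.5.2) | Not stated | Yes, at that visit, but not as one patient count across visits |
| Ultrasound listing (SAP 5.3.5.2) | Reader must do it by hand | Yes, but untabulated |
| AE and special-interest tables (SAP 5.3.2, 5.3.2.1) | Treatment-emergent events only | Only if recorded as an AE |

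The by-visit summary cannot stand in for an any-time count. Exclusion criterion 8 (Protocol 5.3) admits patients with asymptomatic cholelithiasis or bile duct dilation, so a visit's percentage mixes old and new findings. The patients scanned also change from visit to visit, so visit counts cannot be added up.

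The AE tables are not a full substitute either. Under Protocol 8.1.1 an abnormal test result is an AE only if it causes signs or symptoms, is considered clinically significant, needs therapy or leads to a change in study medication. An incidental stone that meets none of these need not be recorded.

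**2. Direction.** Code each ultrasound item as normal or abnormal and take a patient who is normal at baseline. If the last on-treatment scan is abnormal, the worst one is too. The reverse need not hold. So

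number shifted (worst) ≥ number shifted (last),

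with equality when no new finding clears before the last scan. For a patient with a single post-baseline scan, last and worst are the same.

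**3. Size.** Let p be the proportion with a new finding at any time and f the share of those whose finding is absent at the last scan. The undercount is p × f. The documents give neither quantity for ultrasound, so the following only shows how the formula behaves.

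- N = 200, the approximate planned size (SAP 4.10.1).
- p = 29.6%, borrowed from Protocol 1.2.2. That is an adverse event rate for cholelithiasis in the earlier phase III study, not an ultrasound rate. 0.296 × 200 = 59.2, taken as 59 patients (29.5%).
- f = 5% to 30%, assumed.

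| f | Shown by last-value shift, 59 × (1 − f) | Not shown | Points |
|---|---|---|---|
| 5% | 56 (28.0%) | 3 | 1.5 |
| 10% | 53 (26.5%) | 6 | 3.0 |
| 20% | 47 (23.5%) | 12 | 6.0 |
| 30% | 41 (20.5%) | 18 | 9.0 |

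The spread comes entirely from the assumed f. Patients with stones at baseline cannot develop new ones under either rule, which is a further reason not to read the table as an estimate.

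**The case against.** The strongest reply is that the plan reports these findings elsewhere and that a last-value shift is a legitimate display of status at the end of treatment. Both parts are right. The sentence before the shift table keeps every scan in a by-visit summary and a listing, and the protocol's statistical section is not contradicted. What the reply does not supply is a planned patient-level count of new ultrasound abnormality.

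A reader might go further in three ways that the documents do not support.

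- *That transient or treated stones vanish from the report, or from its main gallbladder display.* No display is named as the main one, and the findings stay in the summary and listing.
- *That the patients missed are the serious ones, those who had surgery.* They have the most other routes into the report. A finding needing therapy is an AE (Protocol 8.1.1). Inpatient hospitalisation generally makes an event serious (8.2.1). Gallbladder events are notified like SAEs (8.2.2), and the SAP tabulates AEs, SAEs and special-interest events (5.3.2, 5.3.2.1). Nor do the documents say how a removed gallbladder is coded. It could have its own category, and if no scan follows surgery the last value is the pre-surgery scan.
- *That the undercount is known to be several percentage points.* Any such figure joins an AE rate from another study to an assumed clearance share.

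It is also fair to say that worst needs defining. Unlike laboratory tests, ultrasound findings have no grade or normal range in the documents.

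**Conclusion.** The point holds as a small reporting gap. The only planned ultrasound display that sets each patient against baseline uses the last on-treatment scan, out of line with the laboratory, vital-sign and ECG analyses in the same SAP. New findings that clear before the last scan are not counted as shifts, and no planned table gives the number of patients with any new finding. The findings most likely to go uncounted are incidental, asymptomatic and transient, because clinically important ones should reach the AE and special-interest tables.

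Given a simple normal/abnormal ordering, the understatement runs one way only. Its size cannot be determined from the documents. The primary variable, drug-related adverse events that are grade 3 or 4 or serious, does not use this table and is unaffected.

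**What to change.** In SAP 5.3.5.2, keep the last-value shift and add one of the following:

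- a shift from baseline to the worst on-treatment value for each ultrasound item, beside the last-value shift, as is already planned for fasting glucose; or
- the number and percentage of patients with at least one post-baseline ultrasound finding not present at baseline, each patient counted once per category, as for ECG.

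The second avoids any grading beyond normal or abnormal. Under either option, state how a gallbladder removed on treatment is categorised (for example abnormal, a category of its own, or not evaluable), because the last-value shift also depends on it.

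The cost is a simple normal/abnormal ordering, one derived variable and an extra column or table. If removal is to be counted, the procedures record must be linked to the ultrasound data. No new data are needed. The displayed rate may be less favourable than under the last-value rule.

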5.4 Patient demographics/other baseline characteristics

Demographic and other baseline data (including disease characteristics) will be summarized descriptively for the FAS.

5.4.1 Protocol deviations

[figure not shown]
The number and percentage of patients with any relevant protocol deviation will be tabulated. All relevant protocol deviations will be listed. Protocol deviation criteria are specified in the Validation and Planning (VAP) document.

5.5 Concomitant therapies

Concomitant medications and significant non-drug therapies prior to and after the start of the study treatment will be summarized by ATC class and preferred term. These analyses will be performed on the safety set.

5.6 Study medication

Descriptive statistics will be used to summarize the mean daily dose and duration of exposure to pasireotide s.c for all patients and by mean daily dose group (see [section 4.8](#)). The actual and planned doses administered and reason for dose change will be listed. These analyses will be performed on the safety set.

7 Data handling conventions

Date imputation for AEs and concomitant medications will be imputed according to Novartis conventions described in [RAP Module 8].

Vital sign Study Completion CMP, ECG and laboratory assessment will be imputed in associating visit date from Visit-based event date imputation (AVIS) (See RAP Module 8).

As describe in the RAP Module 8, any event which has a partial date and requires imputing but has no specific imputation rule, is imputed as follows:

- if the day and month is missing, it will be replaced by 1st of July
- if only the day is missing it will be replaced by the 1st of that month. Partial dates will remain partial in the data listings.

8 Adverse Events of Special Interest (MedDRA v 19.0)

Adverse events of special interest will use MedDRA v 19.0 or the latest version available at a time of data base lock. The current version of grouping of adverse event is present in an attached spreadsheet. The latest version of this spreadsheet will be used at the time of database lock.

SOM230_AESI_Med
DRA 19.0_22Apr2016

The adverse events of special interest list for SOM230 based on MedDRA version 19.1 is available on CREDI:

/CREDI Projects/S/SOM230C/Administrative files/CIS (Clinical Information Sciences)/Biostatistics - SOM230_AESI_MedDRA 19.1_21Nov2016.xls

https://webedi02.eu.novartis.net:8443/webEDI02_non_SSO/drl/objectId/090095a88a122b51

9 References

American Diabetes Association, (2010), 'Diagnosis and Classification of Diabetes Mellitus', *Diabetes Care*, 33, Supplement 1, S62-S69.

Clopper, C. J., and Pearson, E. S. (1934), 'The Use of Confidence or Fiducial Limits Illustrated in the Case of the Binomial', *Biometrika* 26, 404–413.

Reilly, M. "www.reillyassociates.net" ©2002 Margaret Reilly Associates, Inc., October 19, 2011, "http://www.reillyassociates.net/WPAI_Scoring.html".
